12.4.1 End of Each 28-day Cycle Contact (Post 52 Weeks + 1 w)

Subjects will be contacted (e.g. phone calls, e-mail or text message) at the end of each 28-day cycle, beginning after the 52-week visit. The cycle is determined from the day of VeraCept insertion:

- Verify sexual activity
- Document any back-up contraception methods

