Investigational

Site Information: This study will be conducted at up to 14 centers in the U.S

Follow-up: Physical assessment (office visit) will occur at weeks 6, 13, 26

and 52 after placement, with monthly telephone contact. For those subjects who wish to continue study device use after 12 months, follow-up office visits will occur every 6 months with contact at the end of each 28-day cycle beginning after the 52-week visit. Additional visits will be conducted if necessary for

safety issues.

Follow-up after early study device removal:

Subjects requesting VeraCept removal to become pregnant will be followed to pregnancy or until the subject changes her mind about trying to get pregnant. All subjects in whom VeraCept is removed prior to 12 months, for any reason, will be required to use an alternative contraceptive for the first two weeks following removal. Hormonal contraceptive pills will be reimbursed by the sponsor as a contraceptive option during this time unless the subject has a category 4 condition precluding their use.

Study Population:

Pre-menopausal women ages 18 – 40, at risk for pregnancy, who are interested in using an intrauterine contraceptive for birth control will be eligible for this study. Subjects must provide written informed consent and meet the study subject selection criteria without any exclusions as outlined in the Clinical Investigation Plan (CIP).

Primary Effectiveness

Outcome:

The primary outcome measure is effectiveness, evaluated as the absence of pregnancy by 12 months, failure will be calculated by the Pearl Index.

Safety and Other Outcome

Measures:

Safety and other outcome measures include:

Study Device Placement:

- Ease of placement
- Placement success

Safety:

- Serious Adverse Events
- Adverse Events

Tolerability:

- Bleeding and spotting patterns
- Discontinuation rate and reasons for discontinuation

Subject Selection Criteria

INCLUSION CRITERIA

Subject must meet all of the following criteria to participate in this study:

- 1. Between 18-40 years of age at the time of study initiation;
 - 1.1 Enrollment will be targeted for 225 subjects aged 18-35 (for safety and effectiveness analyses) and an additional 25 subjects aged 36-40 (for safety only) (note: all subjects will be included in the analysis for device placement and tolerability);
- 2. Pre-menopausal, as determined by regular menstrual cycle (28 ± 5 days) for the last 3 months;

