- Transvaginal ultrasound to document VeraCept position
- VeraCept Removal
 - VeraCept removal ease
 - VeraCept removal pain
- Urine pregnancy test will be done 17 days after removal/study exit by the subject at home, with a follow up call by the study coordinator or PI required to document results.

At 52 weeks, subjects will be allowed to continue with the study device with an office follow-up visits every 6 months for a maximum of three years post study device placement).

A 2-week supply of hormonal contraceptive pills will be provided to the subject by the site as a contraceptive option for the first two weeks after VeraCept removal.

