12.3.1 Monthly Phone Contact (up to 52 Weeks)

Subjects will be contacted by phone each month, after her menses, to confirm completion of the monthly diary for:

- The need for additional contraception;
- Use of concomitant contraception;
- Use of concomitant medications;
- Documentation of menstrual and intermenstrual bleeding;
- Assess if there have been any adverse events since the last contact; and
- Resolution of any prior serious adverse events or adverse events.

12.4 Long-term Follow-up post 52-week visit (Every 6 Months: Months 18-30 (±4wks) and 3 yrs (-3wks/+4wks) /Exit visit

The subject will return for follow up after their Week 52 visit, every 6 months, if they choose to continue with the study visit. During these visits, the subject will be evaluated for:

- Vital signs and weight
- General physical exam (same as at Screening Visit)
- Pelvic exam (string check)
- Transvaginal ultrasound to document VeraCept position (only if indicated)
- Pregnancy test, urine
- Interval and concurrent medications
- Adverse events
- Verify sexual activity

Document any back-up contraception methods

Additionally, at the final visit at 3 Years / Exit visit, the following will also be performed:

- Transvaginal ultrasound to document VeraCept position
- VeraCept Removal
- Urine pregnancy test will be done 17 days after removal/study exit by the subject at home, with a follow up call by the study coordinator or PI required to document results.

A 2-week supply of hormonal contraceptive pills will be provided to the subject by the site as a contraceptive option for the first two weeks after VeraCept removal.

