15. ADVERSE EVENTS AND SERIOUS ADVERSE EVENTS

During the study, the Investigator or study site personnel will be responsible for querying and recording adverse events (AEs) and serious adverse events (SAEs), as detailed below. Subjects will also be required to record AEs on their daily diary. For the Sponsor to fulfill safety assessment obligations, the Investigator must report all SAEs to the Study Sponsor, whether or not they result from study participation, within 24 hours of learning of the event.

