15.11 Post-Study Treatment Reporting Requirements

For all enrolled subjects, all AEs and SAEs, regardless of cause or relationship, that occur from the beginning of study device placement through Study Exit require reporting to the Sponsor. In addition, if the Investigator learns of any SAE at any time after a subject has had the study device removed, and such event seems reasonably related to study drug, the Investigator should immediately notify the Sponsor.

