## 3.7.2 Efficacy Analyses for the Whole Study

Post-Year 1 sexual activity and contraceptive use information can be found in the Cycle Contact CRF, which was added since the Extension study (Year 2) started, i.e., this CRF wasn't present from the beginning of the study, but added as a mid-study change. Each record in this form is for one cycle and has the following 2 key questions for determining if a cycle is pregnancy-risk or not:

- Did the subject have intercourse at least once during the cycle? (Yes, No)
- Did the subject use backup contraception during the cycle? (Yes, No)

If the answer is "Yes" to the first question and "No" to the second question, or the subject was pregnant within a cycle (determined form the Pregnancy Test form), that cycle will be considered as a pregnancy-risk cycle; otherwise, the cycle will not be considered as a pregnancy-risk cycle.

For cycles without any Cycle Contact information, e.g., neither of the above 2 "Yes"/"No" questions were answered and a subject wasn't pregnant within the cycle either, the following procedure will be used to do the estimate for the subject:

- A. find the total number of such type of cycles for that subject
- B. find proportion of pregnancy-risk cycles from Year 1 diary data of the subject, which will be calculated as the number of pregnancy-risk cycles divided by the total number of cycles from Diary CRF
- C. The number from Step A is multiplied by the number from Step B, and then rounded to 1 decimal place, which will be the estimated number of pregnancy-risk cycles where Cycle Contact information is missing for the subject.

The number from Step C will be added to the number of pregnancy-risk cycles from those without missing Cycle Contact information, and then added to the Year 1 pregnancy-risk cycles from Diary CRF data to get denominator value of the Pearl Index for Year 2 (data cut off at 26 cycles) and Year 3 (data cut off at 39 cycles). The numerator will be the number of on-treatment pregnancies by the end of Cycle 26 and Cycle 39, respectively.

The Year 2 and Year 3 analyses will also be performed without inclusion of cycles with missing Cycle Contact information, i.e., not doing estimates of pregnancy-risk through the above Steps A, B, and C.

The 95% Confidence Intervals for the Pearl Index will be calculated, by using the formula in the above Section 3.7.1, at the following 3 scenarios:

- All EP subjects
- EP subjects with at least one live birth

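### After Week 52 scheduled adverse event enquiry drops from about 16 a year plus a daily diary to 2 a year, yet the SAP tabulates AEs by year without a caveat, and the Day 17 call after removal asks only for a pregnancy test

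*Protocol*

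**What the plan says.** **Year 1.** The Investigational Plan Summary (Follow-up) sets the visits: "Physical assessment (office visit) will occur at weeks 6, 13, 26" and 52. Protocol 12.3 lists adverse events and a string check at each. The monthly call in Protocol 12.3.1 must "Assess if there have been any adverse events since the last contact; and" establish whether earlier events have resolved. Protocol 15 adds that "Subjects will also be required to record AEs on their daily diary", and the diary in Protocol 13 has a daily expulsion item.

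**Years 2-3.** Protocol Table 1 dispenses no diary after Visit 5 and last collects it at Week 52. The monthly call also ends then. It is replaced by a 28-day contact (Protocol 12.4.1): "Subjects will be contacted (e.g. phone calls, e-mail or text message) at the end of each 28-day cycle, beginning after the 52-week visit". That contact has two items: verify sexual activity, and "Document any back-up contraception methods". The Table 1 column for this contact has no AE mark; the Year 1 monthly-call column has one. AEs and the string check remain at the six-monthly visits (Protocol 12.4).

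**After removal.** A home pregnancy test is done 17 days after removal or exit, "with a follow up call by the study coordinator or PI required to document results" (Protocol 12.3, repeated in 12.4 and in footnote 4 of Table 1). Protocol 15.11 covers AEs and SAEs "that occur from the beginning of study device placement through Study Exit require reporting to the Sponsor". Later events are covered only if they are SAEs that the investigator learns of and that seem related.

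**Analysis.** SAP 3.8.2 plans AE tables for Year 1, Year 2 and Year 3, and tabulates dyspareunia and allergy-related symptoms by year of onset. It does not mention the change in how AEs are collected.

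**The concern.** When the way of asking changes at the same time as the reporting year, the by-year tables mix two things: how often events occurred and how often anyone asked. Dyspareunia and allergy-related symptoms, which the SAP singles out by year, can be mild and short-lived, and such events are the easiest to lose over a six-month recall interval.

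Expulsion is a smaller version of the same issue. Protocol 4.6 does not require routine string checks. In SAP 3.7.2 a cycle in Years 2-3 counts as at risk on two answers, intercourse yes and back-up no; neither asks whether the device is still in place. An expulsion that the woman does not notice may be dated late. That affects the exposure count and the rule that attributes pregnancies conceived within 7 days of expulsion.

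After removal, pelvic infection and pelvic inflammatory disease are on the list of events of special attention in Protocol 20.7. No scheduled contact asks about new events in that period, although a call is already made.

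**Working it through.** The documents give no AE or expulsion figure to reproduce, so the check counts scheduled enquiries and measures the SAP's windows.

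**1. Scheduled AE enquiries per year**

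| Period | Visits with AE enquiry | Calls or contacts with AE item | Total per year | Daily diary |
|---|---|---|---|---|
| Year 1 | 4 (Weeks 6, 13, 26, 52) | about 12 | 4 + 12 = 16 | yes |
| Years 2-3, as written | 2 | 0 of 13 | 2 | no |
| Years 2-3, with an AE item added | 2 | 13 | 2 + 13 = 15 | no |

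The drop is 16 / 2 = 8-fold before the diary is counted. SAP 3.7.2 cuts the data as "Year 2 (data cut off at 26 cycles) and Year 3 (data cut off at 39 cycles", and SAP 2.4.1 equates 12 months with 13 cycles. That makes 39 - 13 = 26 contacts in Years 2-3 without a listed AE item.

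**2. Gap between device checks.** Six months is about 26 weeks, or 26 / 4 = 6.5 cycles. With windows of 4 weeks either side, two successive visits can be 183 + 56 = 239 days apart, about 34 weeks or 8.5 cycles. This bounds the time to a scheduled check. It does not measure false exposure, because SAP 3.7.1 ends exposure at the expulsion date.

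**3. What recall alone could do (assumption; the documents give no recall figure).** Suppose events occur at a constant rate and are forgotten with half-life h months. With k = ln 2 / h, the share still reported over a recall interval T is (1 - exp(-kT)) / (kT). Take T = 28/30.4 = 0.92 months for a monthly call and T = 6 for the long-term visits. For h = 3, k = 0.231: the six-month share is (1 - 0.25) / 1.386 = 0.541, the monthly share is 0.901, and the ratio is 0.60.

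| Half-life (months) | Monthly share | Six-month share | Apparent Year 2 / Year 1 ratio |
|---|---|---|---|
| 1 | 0.739 | 0.237 | 0.32 |
| 3 | 0.901 | 0.541 | 0.60 |
| 6 | 0.949 | 0.721 | 0.76 |
| 12 | 0.974 | 0.845 | 0.87 |
| 24 | 0.987 | 0.918 | 0.93 |

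The diary is left out of this illustration. Including it would raise Year 1 capture and lower each ratio.

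**4. Denominator.** SAP 3.1.3 bases AE percentages on the total size of the population, and no year-specific at-risk count is stated. If 50% to 90% of subjects continue (assumed), a fixed Safety denominator multiplies the Year 2 percentage by a further 0.5 to 0.9.

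**5. Year windows in SAP 3.8.2.** Year 2 runs from Day 366 to 730: 730 - 366 + 1 = 365 days. Year 3 is written as Day 371 to 1095: 1095 - 371 + 1 = 725 days, which is 725 / 365 = 1.99 times as long. The overlap with Year 2 is 730 - 371 + 1 = 360 days. This pushes the Year 3 counts up, against the two effects above.

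**The case against.** The strongest case on the other side is that AE collection does not stop. Each six-monthly visit lists adverse events (Protocol 12.4), every AE through Study Exit must be recorded (15.2, 15.8, 15.11), and unscheduled visits are documented (12.6). SAEs and AEs that lead to removal are much less exposed to recall. After removal, known AEs are followed for up to 30 days (12.5, 15.9), and events during the removal procedure are recorded (15.3.1). The 1-year analysis is the main one (SAP 3.1.2); Years 2-3 are optional and secondary. The SAP calls the two contact questions key ones, so the form may hold others. All of this stands, and it narrows the point to non-serious events, expulsion dating and new events after removal.

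Two stronger readings are tempting, and the documents do not support them.

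- *Any fall in AEs after Week 52 is an artefact.* Real declines are also plausible. Year 1 contains placement, and Protocol 6.2 lists procedural pain and post-procedural haemorrhage among its events. Women who tolerate the device poorly can leave before the extension. The Year 3 window as written need not show a fall at all.
- *The expulsion rate will appear to fall, or up to 6.5 cycles of false exposure accrue per unnoticed expulsion.* The planned rates are cumulative, over subjects still in the study (SAP 3.8.3, 3.8.4). String checks continue, women are told to call if they suspect expulsion (Protocol 4.6, 12.7), and the plan refers to a calculated expulsion date. Only dating error, or an expulsion never detected, adds false exposure.

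**Conclusion.** The point holds in a limited form. The drop from about 16 scheduled AE enquiries a year plus a diary to 2 a year is a matter of record, as is the absence of an AE item on the Day 17 call. The consequence is a risk of under-recording non-serious, transient events in Years 2-3, of late or imprecise expulsion dates, and of missing new non-serious events after removal. Its size is unknown. The ratios of 0.32 to 0.93 rest wholly on assumed half-lives and show only that the effect could be large or slight.

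The firm conclusion concerns interpretation: ascertainment is unequal between Year 1 and Years 2-3, the denominator may not reflect who is still at risk, and the Year 2 and Year 3 windows overlap. A difference between the by-year tables, in either direction, cannot be read as a change in tolerability. The conclusion assumes that the contact form holds no AE field beyond what the protocol lists. The primary 12-month Pearl Index is not affected.

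**What to change.** **Protocol, if follow-up is still running**

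- Add two yes/no items to the 28-day contact: any new or worse health problem since the last contact, and any sign that the device is out or displaced. Route a yes to the existing AE form or unscheduled visit.
- Add the AE item to the Day 17 call, and extend the recording window in 15.2, 15.8 and 15.11 to that call. A device-presence item has no place there.

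**SAP, in any case**

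- Footnote the by-year AE tables, and those for dyspareunia and allergy-related symptoms, with the ascertainment method in each year and the date of any change.
- Show subjects or person-time at risk in each year.
- Reconcile the Year 3 start (Day 371) with the Year 2 end (Day 730).
- List AEs with onset after removal separately.

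**Cost.** A short amendment and a few form fields on contacts already made, with no extra visit. Expect some extra AE forms and higher late AE counts. Adding the items partway through the extension creates a further change of ascertainment within Years 2-3, which is why its date belongs in the footnote. If the data are already collected, only the SAP changes apply.

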12.5 Early Discontinuation Visit

Subjects who request removal of VeraCept before 12 months will be required to use an alternative contraceptive for the first two weeks following removal. A two-week supply of Hormonal contraceptive pills will be provided by the site as a contraceptive option during this time.

If a subject requests VeraCept removal because of an adverse event, the Study Exit Visit described in Section 12.3 above should be completed and documented on the CRF at the time of VeraCept removal. The subject will be followed until resolution of the event or 30 days after removal, whichever occurs first. Subjects experiencing an on-going adverse event will continue to receive the appropriate follow-up medical care.

If a subject requests early discontinuation and VeraCept removal to become pregnant, the Study Exit Visit described in Section 12.3 above should be completed and documented on the CRF at the time of VeraCept removal. Additionally, subjects shall be followed for either; six (6) months, until they decide to no longer try to conceive or they become pregnant, whichever comes first. Outcome data regarding subject's ability to conceive, or the decision to no longer try to become pregnant will be collected via phone contact and documented on the phone contact form.

12.6 Unscheduled Visits

Unscheduled visits must be documented on a follow-up visit CRF. Medical evaluations will be conducted as indicated by the reason for the unscheduled visit.

12.7 Emergency Contraception

If the subject suspects the VeraCept has expelled, she should contact the study site. Emergency contraception may be administered, according to product labelling, if the subject suspects expulsion has occurred and an act of intercourse might be unprotected, and she does not want the risk of pregnancy. If the subject is subsequently found to have an *in situ* IUD and desires to continue in the study, the cycle during which she used EC will not be included in the analysis unless the subject conceives. If the IUD is expelled, she will be exited from the study.

13. Diaries

Subjects will be instructed to complete diaries daily. Diaries are designed to collect the following information for each day of each menstrual cycle:

- Day of cycle
- Date
- Absence or presence of menstrual or other bleeding (none, spotting, normal or heavy)
- VeraCept expulsion (yes, no, suspected)
- Usage of additional birth control methods and type of birth control used
- Presence of abnormal pain or cramping
- Other medical problems
- All medications taken that day
- Frequency of intercourse
- Liner, pad and tampon usage

14. CONCOMITANT MEDICATIONS

Concomitant medications include any medication or health product (any prescription medications or over-the-counter preparations) taken from the time the subject signs the informed consent documents until Study Exit and must be recorded appropriately on the eCRF.

15. ADVERSE EVENTS AND SERIOUS ADVERSE EVENTS

During the study, the Investigator or study site personnel will be responsible for querying and recording adverse events (AEs) and serious adverse events (SAEs), as detailed below. Subjects will also be required to record AEs on their daily diary. For the Sponsor to fulfill safety assessment obligations, the Investigator must report all SAEs to the Study Sponsor, whether or not they result from study participation, within 24 hours of learning of the event.

15.1 Definition of a Serious Adverse Event

A **serious adverse event (SAE)** is any adverse event occurring within the timelines specified in the protocol that results in any of the following outcomes:

- Death:
- Life-threatening situation (subject is at immediate risk of death);

- Inpatient hospitalization or prolongation of existing hospitalization;
- Persistent or significant disability/incapacity;
- Congenital anomaly/birth defect in the offspring of a subject who received study device; or
- Important medical events that may not result in death, be immediately life-threatening, or require hospitalization, may be considered an SAE when, based upon appropriate medical judgment, they may jeopardize the subject and may require medical or surgical intervention to prevent one of the outcomes listed in this definition. Examples of serious adverse events include, but are not limited to: intensive treatment in an emergency room, hospitalization for any reason, and extensive treatment at home for an adverse event. An ectopic pregnancy is considered a serious adverse event.

15.2 Definition Of An Adverse Event

An **adverse event** is any untoward medical occurrence in a clinical investigation subject administered an investigational product and which does not necessarily have to have a causal relationship with this treatment. An AE can, therefore, be any unfavorable and unintended sign (that could include a clinically significant abnormal laboratory finding), symptom, or disease temporally associated with the use of a medicinal product, whether or not considered related to the medicinal product.

- Any medical condition or clinically significant laboratory abnormality with an onset date before the first date of attempted study device placement is usually considered to be pre-existing, and should not be documented in the eCRF as an AE, unless there is an increase in frequency or intensity of that AE, but should be recorded as medical history.
- Any AE (i.e., a new event or an exacerbation of a pre-existing condition) with an onset from the first attempt of study device placement through Study Exit should be recorded as an AE on the eCRF. All AEs must be recorded on the AE eCRF regardless of the severity or relationship to study device. It is important that Investigators also report all AEs that result in expulsion or removal of the investigational product being studied, whether serious or non-serious.

Pregnancy is an outcome, and not an adverse event in this study.

